effects. In addition, preemptive testing allows genotyping samples from many patients to be batched and run in high volume, which substantially decreases the genotyping cost per patient. Thus, the most feasible/sustainable way to facilitate the clinical implementation of PGx in underserved patients will likely involve preemptive genotyping.

To our knowledge, there have been no studies reporting implementation data of preemptive PGx testing in medically underserved patients. Further, there are few data in the literature regarding the perceptions and attitudes of black and Latino patients toward preemptive PGx testing. This work is significant because it is expected to contribute valuable data toward both the feasibility of preemptive PGx testing in medically underserved patients, an area of PGx research where little information is available. We anticipate these data will inform future multi-site clinical trials of preemptive PGx implementation.

5. Specific Aims:

Motivated by the critical need to expand access of preemptive PGx testing to underserved populations, the overall objective for this application is to develop key feasibility data to equitably advance preemptive PGx testing within UF Health, and to generate important preliminary data to support future funding applications. The rationale for this project is that generating these feasibility data should facilitate equitable clinical implementation that may reduce medication treatment disparities, as well as inform future larger clinical studies. We plan to accomplish the overall objective of this application by pursuing three specific aims:

1. Assess the feasibility of preemptive PGx clinical implementation in primary care clinics predominantly serving medically underserved patients. We will provide clinical preemptive PGx testing for 100 patients from specific UF Health clinics serving mostly medically underserved patients, including clinics with a high rate of black and Latino patients. We will assess feasibility of this implementation effort by comparing patient-reported outcomes data abstracted from electronic health records before and 6 months after PGx testing.

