2. Understand perspectives on preemptive PGx testing among key stakeholders in the primary care clinics predominantly serving medically underserved patients. We will conduct in-depth, semi-structured interviews with a subsample of recruited patients from Aim 1 and clinicians within the clinic sites to identify influential factors critical to implementing PGx testing, including motivations, barriers, and best practices for the delivery of results.

3. Identify specific socioeconomic characteristics most strongly associated with PGx drug prescription rates. Our preliminary data using EHR data from UF Health show strong correlations between zip code-derived healthcare geographic access scores and rate of PGx drug prescriptions. We aim to use the results of a validated socioeconomic estimation tool as well as individual measures of socioeconomic status in a single predictive model to determine which social determinants most associate with PGx drug prescription rate within the 100 patients from Aim 1.

6. Research Plan:

Study population and setting. This study will include UF Health patients recruited from clinics that serve mostly medically underserved areas. Primarily, this will include the UF Health Family Medicine Eastside and Main St. Clinics, which serve a large number of low-income, black and Latino patients. Overall, we plan to recruit 100 patients from targeted clinics. Inclusion criteria are designed to identify patients who have a high possibility of benefitting from PGx testing.

Inclusion Criteria:

1. Adults (18 years or older) with active prescriptions for at least 3 medications documented within the EHR.
2. At least 1 drug/drug class that could be informed by the PGx test panel (See Appendix A for complete list).
3. A medication change within the past 6 months (associated with a healthcare provider encounter)
4. Self-identify as black or Latino.

Exclusion Criteria:

1. Patients with any history of PGx testing within the EHR.

Participant Recruitment Methods.

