Patients may be approached for the study in various way including clinic intercepts, study flyers and clinic referrals. The electronic health record will be queried to identify potentially eligible participants using the inclusion/exclusion criteria. Providers (including but not limited to physicians, nurse practitioners, and pharmacists) who care for patients at UF Health will be notified when their patients qualify for the study and will be asked to discuss the study with their patients.

Patients can be recruited by study staff via two methods:

1. Clinic providers or staff ask patients if they are interested in participating and they acknowledge that they are interested.
2. Clinic provider or staff will provide patients an approved flyer and they contact study staff if interested.

If recruitment occurs during a clinic visit, patients meeting eligibility criteria will be approached by a research coordinator about study participation. Patients may also be contacted via phone after their clinic visit if in-person contact is not possible (for example, but not limited to, space limitations due to COVID-19 restrictions).

A research coordinator will review the consent document with the patient prior to enrollment. The consenting process can be in-person or remote via telephone or through electronic means. Prospective research participants will have the opportunity to ask questions before providing consent and will be provided with a signed copy of the consent form.

After providing written informed consent, a DNA sample will be collected from all patients by saliva (via mouthwash swish and expectorate collection) or buccal cell (via buccal brush/swab). If the genotyping fails with initial sample collection, the patients may be mailed a DNA collection kit for saliva or buccal cell sample collection for retesting.

Study design. After eligible participants provide written informed consent and are enrolled, a DNA sample will be obtained for PGx testing and questionnaires (as described below) will be administered at baseline, and then again at 3 months and 6 months after PGx results are entered into the EHR. Information will be abstracted from the EHR including PGx test results, medication changes, and healthcare provider encounters over the 6-month study duration (Table 1). A 1-month window will be permitted for each follow-up study interaction (\pm 15 days of exact due date).

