PGx testing will be completed using the GatorPGx panel, which is already available for clinical use in the CAP/CLIA certified UF Molecular Pathology Laboratory. Once results are entered into the EHR, Clinical Decision Support Best Practice Advisories already built into Epic will alert providers if a PGx interaction

might occur with a medication they prescribe. All clinical medication decisions will be made at the discretion of the healthcare provider.

Feasibility data collection:

The primary feasibility outcome will be change in patient treatment satisfaction between baseline and 6 months after PGx testing. This patient reported outcome will be measured via the Treatment Satisfaction Questionnaire for Medication (TSQM). The TSQM is a validated tool that assesses three medication-related domains (effectiveness, side effects, and convenience) to synthesize a global satisfaction score.^{5,6} Both global satisfaction and scores from individual domains will be analyzed.

Table 1. Proposed outcomes/measures to be tested

Outcome/Measure	Data source/Instrument	Ascertainment method	Baseline	3 mo.	6 mo.
Implementation Outcomes					
Treatment satisfaction	Treatment Satisfaction Questionnaire for Medication (TSQM)	Online or by phone	X	X	X
Medication adherence	Adherence Questionnaire	Online or by phone	X	X	X
Perceived value	Patient reported value	Online or by phone	X	X	X
Time discussing meds w/ healthcare provider	Patient reported estimate	Online or by phone	X	X	X
Effectiveness Outcomes					
Medication changes	EHR data	EHR data pull	X		X
Provider encounters	EHR data	EHR data pull	X		X
Socioeconomic Measures					
SEI	Patient report	Online or by phone	X		
Occupation	Patient report	Online or by phone	X		
Education level	Patient report	Online or by phone	X		
Household Income	Patient report	Online or by phone	X		
Household zip code	Patient report	Online or by phone	X		

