An important secondary outcome assessing efficacy will include the number of medication changes within the 6-month follow-up period. Medication changes will be defined as the addition, removal, or dosage change to any PGx medication or medication within the same drug class. Comparisons of this outcome should estimate differences in trial-and-error drug dosing that is traditionally used in practice. These outcomes are important because if the results suggest that preemptive PGx testing is associated with increased patient treatment satisfaction, a reduction in medication changes, or increased perceived value of PGx testing, these findings would support expanded clinical implementation in medically underserved patients. This might also suggest that PGx could be further used as a tool to minimize disparities in pharmacotherapy. Other secondary outcomes that will be analyzed include: The prescriber acceptance rate of PGx EHR alert recommendations, number of encounters with a healthcare provider over the study period, genotype turnaround time, and estimated time spent discussing medications with a healthcare provider. These outcomes will be used to assess feasibility and will inform design of a large clinical trial to be funded by future grants.

Socioeconomic data collection: We have previously observed significant associations between calculated geographic access scores and rate of PGx drug prescriptions, which considerably strengthened in subanalyses by race. Whether this association is exclusively related to geography and race or whether it is also related to socioeconomic determinants is unknown. Thus, we will test whether socioeconomic status is a social determinant of health related to PGx drug usage. Patients will answer survey questions related to their education, employment, and income (Table 1).

Qualitative data collection: An estimated sample size of 20 patients from the 100 recruited participants will be recruited for this aim. Patient sampling will be aimed at achieving an approximately even distribution of sex (male and female) and race (Latino and black).

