Analysis plan. For Aim 1, implementation outcomes such as prescriber acceptance, turnaround time, and cost will be assessed using descriptive statistics. Differences in patient reported outcomes such as treatment satisfaction, perceived value, and effectiveness outcomes (Table 1) will be initially compared between baseline and 6 months using Student's t-test or Mann-Whitney U test, depending on the data distribution. In addition to univariate analyses, multiple regression models will also be completed for each outcome, adjusted for potential covariates, such as age, race, sex, clinic site, and Charlson Comorbidity Index. In all analyses, a two-sided $P \leq 0.05$ will be considered statistically significant, and all statistical analyses will be completed in R ver. 3.6.3.

For Aim 2, interview transcripts will be managed using data management software (e.g., Nvivo or Atlas.ti). Data will be thematically analyzed using the widely used constant comparative method.¹³ This systematic approach involves several coding steps including identifying concepts and assigning codes, 2) grouping categories of emergent themes, and 3) axial coding to identify thematic properties. To ensure similarities and differences between patients' experiences can be captured, data analysis will be segmented by group and triangulated with survey data collected from healthcare providers (via separate protocol). Triangulation of data between sources also enhances the validity of the findings.¹⁴ Multiple coders, trained in the CCM approach, will conduct the analysis to ensure rigor. Meetings will be held to compare independent coding, discuss differences in interpretation, collapses analyses, and continuously refine the codebooks. Codebooks will be developed with each stakeholder group dataset. Once codebooks are finalized and analyses complete, each analysis will be validated by an additional coder analyzing a subset of the transcripts from each group.¹² Operational and thematic memos will be maintained across data collection and analysis to ensure researcher reflexivity, thematic saturation, and rich description of themes.

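### The primary TSQM result is an uncontrolled before-after change in patients with a recent medication change, so a rise cannot by itself support wider PGx implementation

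*Combined protocol and SAP*

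**What the plan says.** Section 6 (Research Plan, Feasibility data collection) defines the outcome: "The primary feasibility outcome will be change in patient treatment satisfaction between baseline and 6 months after PGx testing". Section 5, Aim 1, sets the size: "We will provide clinical preemptive PGx testing for 100 patients from specific UF Health clinics". Under Participant Recruitment Methods, "a DNA sample will be collected from all patients by saliva" or buccal cells, so everyone enrolled is tested. No untested, delayed-testing or historical group is described.

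The third inclusion criterion is: "A medication change within the past 6 months (associated with a healthcare provider encounter". The second requires at least one drug or class covered by the panel. It does not require a genotype that calls for action.

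The Analysis plan says that patient-reported outcomes "will be initially compared between baseline and 6 months using Student's t-test or Mann-Whitney U test, depending on the data distribution", at a two-sided 0.05 level. In addition, "multiple regression models will also be completed for each outcome, adjusted for potential covariates". The examples given are age, race, sex, clinic site and Charlson index.

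The text after Table 1 gives the inference. If testing is associated with higher satisfaction, fewer medication changes or higher perceived value, "these findings would support expanded clinical implementation in medically underserved patients". It adds that PGx might serve as a tool to reduce disparities in pharmacotherapy. The same paragraph says that the outcomes assess feasibility and will inform a larger trial.

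**The concern.** In a single group where everyone is tested, the only evidence that satisfaction is associated with testing is that it moved over time. The entry criterion makes movement plausible without the test. Patients enter within 6 months of a medication change, some may still be adjusting, and a low baseline score would tend to return towards its usual level. Being asked the same questions at 3 and 6 months may also shift answers.

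At stake is what a significant rise allows the investigators to say. As written, it would count towards wider roll-out and a statement on disparities, even if the same rise would have occurred without any genotyping. The same estimate would feed the design of the later trial, where drift mistaken for effect would give too small a sample size.

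**Working it through.** **Inputs from the protocol.** n = 100 (section 5, Aim 1); two-sided 0.05 (section 6, Analysis plan). No effect size, SD, power or dropout is stated, so there is no planned figure to reproduce. Drift, correlation and actionable share below are assumptions.

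**1. Drift with no test effect, paired analysis.** Let δ be the drift in SDs of the change score. The paired t statistic has 99 df and noncentrality δ × √100 = 10δ. It is significantly favourable above 1.984, that is, for an observed mean change above about 0.198 SD.

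| Assumed drift δ | 10δ | P(significant rise), 100 pairs | 80 pairs (assumed dropout) |
|---|---|---|---|
| 0 | 0 | 2.5% | 2.5% |
| 0.1 | 1 | 17% | 14% |
| 0.2 | 2 | 51% | 42% |
| 0.3 | 3 | 84% | 76% |

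**2. If the test is run unpaired.** The Analysis plan does not state pairing. At an assumed correlation of 0.5, the SD of change equals the SD of the score. The unpaired test uses a standard error of √(2/100) = 0.141 where the true one is 0.1, so a rise must exceed 1.96 × 0.141 = 0.277. Φ((δ − 0.277)/0.1) gives about 4%, 22% and 59% for the three drifts. These are lower, but drifts of 0.2 and 0.3 SD still give far more than 2.5%.

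**3. Regression to the mean alone.** Suppose baseline scores average k = 0.5 score SD below their usual level, with correlation ρ. The drift is k(1 − ρ)/√(2(1 − ρ)) SDs of change: 0.25 at ρ = 0.5 and 0.16 at ρ = 0.8. By the normal approximation, Φ(10δ − 1.96) is 71% and 35%.

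**4. Downward drift.** If a true effect of 0.3 SD met a drift of −0.2 SD, the mean change would be 0.3 − 0.2 = 0.1 SD. The chance of a significant rise would be 17% instead of 84%.

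**5. Why the covariates do not help.** Write each patient's change as a constant plus covariate terms plus error. Every patient is tested and every patient is followed over time, so the constant is the sum of the test effect and the common time effect. Age, race, sex, site and Charlson index describe patients and cannot split that sum.

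**6. What an internal contrast would add.** Compare patients whose genotype is actionable for a drug they take at baseline with the rest. Drift common to both groups cancels. The standard error of the difference in change is √(1/n₁ + 1/n₀) SD; at 30 and 70 patients it is 0.218. Adjusting for baseline at correlation 0.5 multiplies it by √0.75. The table gives power for a true 0.5 SD effect in actionable patients only (normal approximation, no drift).

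| Assumed actionable share | Pooled change | Contrast of change | Baseline-adjusted contrast |
|---|---|---|---|
| 20% | 17% | 52% | 64% |
| 30% | 32% | 63% | 75% |
| 50% | 71% | 71% | 82% |
| 75% | 96% | 58% | 71% |

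The contrast has its own weakness. With 30% actionable, no test effect, and extra drift of 0.1, 0.2 or 0.3 SD in actionable patients only, Φ(extra drift/0.218 − 1.96) gives a false favourable contrast of change 7%, 15% or 28% of the time.

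**The case against.** **It is a declared single-arm pilot.** The wording is that testing is associated with a rise, and that findings support expansion rather than prove benefit. Satisfaction is one of three alternatives, and the results are to inform a larger trial. This stands as a reason for moderation. It does not rescue the inference, because the association itself can only be a before-after change, and the sentence goes on to implementation and disparities.

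**Drift is conjecture.** The qualifying medication change need not involve a panel drug or follow dissatisfaction, and may have settled before baseline. This also stands: neither size nor direction is known. The point is that the design cannot tell.

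**A reader might infer that pooling all tested patients is itself an error, since it dilutes any effect in those with an actionable result.** The protocol does not support that. Aim 1 concerns testing in a clinic population, so the average over everyone tested is a legitimate programme-level quantity. Testing is also preemptive. The Background has results stored for later prescribing, and alerts act on whatever a provider prescribes, so a patient with no actionable drug at baseline can still benefit during follow-up.

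**A reader might also infer that the internal contrast should be the sole basis for any statement about PGx testing.** That goes too far. Actionable status depends on which and how many panel drugs a patient takes, and patients on a drug that suits their genotype poorly may drift differently even without the test. The contrast is confounded in another way, and at high actionable shares it has less power than the pooled test.

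**Conclusion.** The concern holds for the inference from the primary outcome. A significant before-after rise in TSQM cannot be separated from settling-in, regression to the mean or repeat questioning, yet the protocol counts it towards expanded implementation. For upward drifts of 0.1 to 0.3 SD of change, the chance of a spurious favourable result is about 17% to 84% with 100 complete pairs and a paired test. These are illustrations under assumed drift, not an estimate of this trial's error rate. The structural argument does not depend on the exact values. The change should be made, but it concerns interpretation and one added analysis. It is no ground for rejecting the single-arm pilot or the pooled mean as a description.

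**What to change.** 1. **Reword the inference after Table 1.** State that a pooled before-after change alone does not support expanded implementation or a disparities conclusion. Report the TSQM change descriptively with a 95% CI, as information for the later trial.

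2. **Add one pre-specified supportive analysis.** Regress the 6-month TSQM global score on an actionable result for an Appendix A drug taken at baseline (yes/no). Adjust for baseline TSQM, age, race, sex, clinic site, Charlson index and number of panel drugs at baseline. Define actionable from genotype and baseline medications only, and fix the definition before outcomes are seen.

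3. **State its limits in the plan.** The contrast is not randomised and removes only drift common to both groups. Patients whose result first matters for a drug started during follow-up count as non-actionable. The interval may be wide: at 30 and 70 patients, 1.96 × 0.218 gives about ±0.43 SD of change before baseline adjustment.

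The cost is analysis-plan wording, one derived variable and one regression. PGx results are already abstracted, and active medications are already reviewed for eligibility in the health record, so no new patients, visits or data are needed. The one real task is writing the definition of actionable, because Appendix A lists gene-drug pairs and not which genotype results count.

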studies. We plan to accomplish this objective by pursuing three specific aims: (1) assess the feasibility of preemptive PGx clinical implementation in primary care clinics predominantly serving medically underserved patients; (2) understand perspectives about preemptive PGx among key stakeholders in the primary care clinics predominantly serving medically underserved patients; and (3) identify specific socioeconomic characteristics most strongly associated with PGx drug prescription rate. To achieve these aims, we will recruit patients for preemptive PGx testing from primary care clinics that primarily serve our target patient population, and use patient-reported outcomes, feedback from semi-structured interviews, and data collected from the electronic health record to assess testing feasibility and pilot outcome data. Upon successful completion of this project, we expect to have generated important preliminary data that can be used to support wider implementation of PGx testing to underserved patients and a variety of current and larger studies designed to further examine implementation of precision medicine technologies. This line of research will positively impact drug-related outcomes by reducing healthcare disparities in the field of precision medicine.

4. Background:

While, for over 30 years, we have known that genetic polymorphisms affect drug response, clinical use of pharmacogenetic (PGx) testing outside of cancer is still not widespread. PGx testing is primarily limited to large academic medical centers, which greatly limits the number of patients who have access to this technology and precision of drug therapy that it allows. In addition, with healthcare costs rising rapidly, there appears to be little appetite for additional reimbursements in our current fee-for-service healthcare model.¹ Thus, many health insurers often refuse to reimburse for PGx tests, especially those done preemptively, requiring the patients to self-pay. This practice excludes low-income patients who are unable or unwilling to incur the out-of-pocket costs. Lastly, many PGx tests have been developed using data primarily from subjects of European descent, making their results less clinically useful for patients of Latino or African descent.

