Current implementation patterns of PGx testing, as with other innovative technologies, have the potential to increase disparities in health care quality and outcomes, especially if there is greater preexisting need in the populations unable to access them. This phenomenon, known as the Inverse Equity Hypothesis,² will continue to occur unless specific access barriers are overcome when a new technology is implemented.

PGx testing may be particularly beneficial in medically underserved populations by reducing the number of medical encounters required to optimize drug therapy and preserving use of less expensive off-patent drugs – the type drugs most often with PGx guidelines available – for patients predicted to benefit based on their genotype results. This is supported by preliminary data from the University of Florida (UF) Health, which indicate that patients with poor geographic access to healthcare providers are prescribed a higher rate of drugs with PGx guidelines available (PGx drugs). Race compounds this disparity, with underserved black patients having both significantly fewer encounters with healthcare providers and more PGx drug prescriptions than underserved non-black patients. Because medically underserved patients use more PGx medications and visit their provider less often, these patients should benefit the most from preemptive PGx testing, where trial-and-error drug selection could be minimized. Thus, there is a critical need to gather data to inform clinical implementation of PGx testing in medically underserved populations to improve healthcare quality and assure equitable distribution of innovative healthcare technologies.

Most experts agree that clinical PGx implementation will eventually evolve to a preemptive testing model where patients are tested for multiple PGx variants at one time, with these data stored in their electronic health record (EHR) to inform future prescribing.^{3,4} Pre-emptive testing is more efficient than “reactive” testing (i.e. at the time of drug prescribing) because most PGx tests have the most clinical benefit when genotype is known before a medication is administered, reducing the risk of treatment failure or adverse

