For Aim 3, total scores and scores within individual domains will be compared with number of medications prescribed, number of healthcare encounters, and PGx drug prescription rate. Comparisons will be completed in univariate analyses via Spearman's correlation test. In addition, multiple regression models will be developed to allow the ability to adjust for potential confounders such as age, and Charlson Comorbidity index. In addition, we will estimate the proportion of variation in PGx prescription rate that can be explained by each socioeconomic measure by comparing coefficients of determination (r^2) in each model.

7. Possible Discomforts and Risks:

Risks involved with participating in this study are minimal, and include accidental disclosure of PHI. To safeguard against this, electronic data will be stored in a custom-designed REDCap database, which is encrypted and password-protected. Paper documents and other physical media will be stored in a

locked cabinet within the PI's locked, private office or the secure Precision Medicine Program research office. Due to the nature of the study, adverse events are not anticipated. However, if any events are observed, they will be reported to the IRB in a manner consistent with UF regulations.

8. Possible Benefits:

Subjects may not directly benefit from participating in this study. There is a possibility of direct benefit to individual subjects, as genotype information could lead to more effective drug prescribing. Nevertheless, in the absence of a direct benefit, the study may advance the field by providing an increased understanding of the utility of preemptive PGx testing in traditionally underserved patient populations. Such understanding is deemed essential for broader dissemination of PGx into clinical care.

9. Conflict of Interest:

The investigators have no conflicts of interest to report. Publications that may result from such research could enhance the reputation of the investigators, but are not expected to affect the conduct of this research.

10. References:

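### Aim 3 ranks socioeconomic measures by their association with PGx drug prescription rate but names no insurance or drug-coverage measure, so the ranking may be incomplete and partly confounded.

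*Combined protocol and SAP*

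**What the plan says.** The protocol's section 5 states Aim 3 as "Identify specific socioeconomic characteristics most strongly associated with PGx drug prescription rates". It plans to put a socioeconomic tool and "individual measures of socioeconomic status in a single predictive model to determine which social determinants most associate with PGx drug prescription rate", using the 100 patients of Aim 1. In section 6, the Analysis plan adds Spearman correlations, multiple regression, and a comparison of r² to estimate "the proportion of variation in PGx prescription rate that can be explained by each socioeconomic measure".

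The candidate measures are set out in two places in section 6:

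- Socioeconomic data collection: "Patients will answer survey questions related to their education, employment, and income (Table 1".
- Table 1, all at baseline and by patient report: SEI, occupation, education level, household income and household zip code. The first and last rows read "SEI Patient report Online or by phone X" and "Household zip code Patient report Online or by phone X". The items that make up the SEI are not described.

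The EHR items named under Study design are PGx results, medication changes and provider encounters. The confounders named for Aim 3 are age and the Charlson index. Both lists are worded as examples, so neither excludes payer data, but no text commits to collecting it.

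**The concern.** A ranking can only order what is on its list. The outcome is the prescribing rate of a group of drugs that section 4 describes as less expensive, off-patent products, "the type drugs most often with PGx guidelines available". If price influences who receives them, what a patient's insurance pays for is a reasonable candidate explanation.

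Without a coverage measure, Aim 3 cannot say whether coverage matters. If coverage also correlates with income, education or occupation, those measures may carry part of its association, and the one ranked first may be standing in for coverage. The pilot is meant to inform larger studies, so an incomplete ranking could influence what those studies measure.

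**Working it through.** **No figure to reproduce.** The plan gives N = 100 and two-sided 0.05, but no effect size, correlation or power for Aim 3. The factual part was settled by reading. Coverage is absent from all four places where it could appear: Table 1, the survey description, the named EHR items and the named confounders.

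**Illustration.** Every effect and correlation below is an assumption.

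*Step 1. One omitted measure.* On standardised variables, with coverage left out,

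apparent income coefficient = b(income) + ρ × b(coverage).

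Take b(income) = 0 and b(coverage) = 0.3. The chance of significance at n = 100 comes from Fisher's z: Φ(atanh(r)√97 − 1.96) + Φ(−atanh(r)√97 − 1.96).

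| ρ (coverage, income) | Apparent coefficient | r² | Chance of P ≤ 0.05 |
|---|---|---|---|
| 0 | 0 | 0 | 5% |
| 0.2 | 0.3 × 0.2 = 0.06 | 0.004 | 9% |
| 0.4 | 0.3 × 0.4 = 0.12 | 0.014 | 22% |
| 0.6 | 0.3 × 0.6 = 0.18 | 0.032 | 43% |

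So 0% to 60% of the coverage effect passes to income over this range. If b(coverage) = 0, nothing passes at any ρ. For scale, the smallest correlation detectable with 80% power is tanh((1.960 + 0.842)/√97) = 0.28.

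*Step 2. Three measures.* Simulated studies with N = 100. Income, education and occupation have no direct effect and correlate 0.5 with each other. The entries give how often at least one of the three reaches P ≤ 0.05.

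| Coverage effect | Correlations of coverage with income, education, occupation | Tested separately (Pearson) | Entered jointly |
|---|---|---|---|
| 0 | any | about 13% | not needed |
| 0.3 | 0.5, 0.4, 0.3 | about 45% | about 26% |
| 0.4 | 0.5, 0.4, 0.3 | about 64% | about 37% |
| 0.3 | 0.3, 0.2, 0.2 | about 25% | not tabulated |
| 0.4 | 0.3, 0.2, 0.2 | about 33% | not tabulated |

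With the planned Spearman test, the separate figures at the stronger correlations are 42% and 61%. The 13% row is the chance level for three correlated tests, so only the excess over it is due to the omission. SEI and zip code are not in this simulation and could absorb some of the effect.

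*Step 3. Would adding coverage help the ranking?* Under these same assumptions coverage, entered as a single-degree-of-freedom measure, has the largest r² in 88% (effect 0.3) and 97% (effect 0.4). That follows from making it the only true driver, so it shows what could be recovered, not what will be.

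*Step 4. A trap in the remedy.* With no true association, the expected r² of a measure with k degrees of freedom is k/(n − 1): 1/99 = 0.010 for a single-df measure and 3/99 = 0.030 for a four-level payer variable. In null simulations against the three single-df measures, the four-level variable came first on raw r² about 67% of the time, where a fair share among four would be near one quarter. Raw r² would therefore favour payer for the wrong reason.

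**The case against.** The strongest case against acting is that this is an exploratory association analysis in a 100-patient pilot. Any socioeconomic list can be lengthened, and the protocol does not single out coverage. That is fair, and it keeps the point to a low-cost improvement.

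A reader might infer that coverage is the factor the protocol's own rationale points to. The documents do not support this. The remark on insurers in section 4, "This practice excludes low-income patients who are unable or unwilling to incur the out-of-pocket costs", concerns payment for the genetic test, and the study provides that test. The remark on off-patent drugs describes a possible benefit of testing and does not mention coverage. The stated reason for Aim 3 is the association of geographic access and race with prescribing, and whether socioeconomic factors also contribute. The link from coverage to PGx drug use is an inference.

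A reader might also infer that the effect of coverage will be credited to income, education or occupation. That requires coverage to have an association of its own and to correlate with those measures. The documents give neither figure.

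Mediation is a further objection that stands. If income determines coverage and coverage affects prescribing, the income association is a genuine total association. Leaving coverage out is then not bias, and adjusting for it answers a different question.

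Finally, the EHR and confounder lists are open, and the SEI may already include coverage. Both are possible, but nothing in the text says so.

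**Conclusion.** The gap is real: Aim 3 orders determinants by strength of association and names no coverage measure anywhere. The ranking may be incomplete, and part of any coverage association may appear under income, education or occupation.

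The size cannot be fixed from the documents. It is nil without an independent coverage association. It is modest at weak correlations, and material only if both the coverage effect and its correlations with the measured items are moderate. That coverage usually tracks income, education and occupation is an assumption from general experience, not a statement in the protocol. On that footing this is a cheap improvement to the aim's ability to answer its own question, not evidence that its result will be wrong.

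**What to change.** First state what the SEI contains. Unless it already covers this, add baseline payer category (for example uninsured, Medicaid, Medicare, commercial) and, where recorded, prescription-drug coverage to Table 1, taken from the planned EHR pull or one baseline survey item.

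In the Analysis plan for Aim 3:

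- enter coverage as a candidate measure alongside the others;
- compare measures on adjusted r², 1 − (1 − r²)(n − 1)/(n − k − 1), or otherwise allow for degrees of freedom, which also matters if education or occupation is analysed in several categories;
- report the other measures with and without coverage, and say in advance whether it is regarded as a confounder or a mediator.

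The cost is one extra field, three degrees of freedom for a four-level variable at N = 100, and a minor amendment to Table 1, Socioeconomic data collection and the Analysis plan. If the field is not added, list its absence as a limitation of the ranking.
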